4.3. Safety Population

The **Safety Population**, used for the assessment of overall safety and tolerability, will consist of all patients who receive at least one dose of study treatment. Patients will be assessed for safety based on the dose level in which they are enrolled.

4.4. Pharmacokinetic Population

The **Pharmacokinetic Population**, used for the assessment of PK endpoints, will consist of all patients who have sufficient RP-6306, irinotecan and/or SN-38 PK concentration data recorded to derive PK endpoints.

For all analysis populations, patients will be presented by the initial dose received.

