This study aims to identify the RP2D and preferred dosing schedule of RP-6306 in combination with FOLFIRI. The DLT evaluation period will consist of 2 cycles (28 days) of treatment. Initially, RP-6306 will be given on a continuous, once daily (QD) schedule (Module 1a) with dose escalation and de-escalation decisions guided by the BOIN drug combination criteria. If necessary, an intermittent dosing schedule (Module 1b) of 3 consecutive days on / 4 consecutive days off may be explored, and Module 1a may be terminated or proceed concurrently with Module 1b. Escalation/de-escalation will proceed independently as guided by the BOIN drug combination criteria. If both modules are run concurrently, patients will be enrolled into either Module 1a or 1b based on available slot openings at the time of signing the ICF and allocated to a cohort by the Medical Monitor with guidance from the SRC.

Module 1a:

The study will start at Dose Level 1 with up to 2 patients receiving 40 mg QD, oral RP-6306 in combination with 180 mg/m² IV irinotecan given over 30 to 90 minutes, 400 mg/m² IV leucovorin given over 30 to 90 minutes with irinotecan, and 400 mg/m² IV fluorouracil bolus after leucovorin, then 2400 mg/m² IV continuous IV of fluorouracil over 46 hours (Days 1 and 2) of each 14-day cycle.

This dose of RP-6306 was chosen based on the observed tolerability and PK of RP-6306 monotherapy in the MYTHIC study. If Dose Level 1 is tolerated, the dose of RP-6306 will be escalated to 120 mg and the dose of irinotecan will be maintained at 180 mg/m² daily (Dose level 2). In addition, patients treated at Dose Level 1 will be eligible to receive RP-6306 at 120 mg QD, if Dose Level 2 has completed the DLT evaluation period and if agreed upon by the SRC. If Dose Level 1 is not tolerated, the dose of irinotecan will be de-escalated to 150 mg/m² and RP-6306 will be maintained at 40 mg daily (Dose level 1D).

After Dose Level 2, dose escalation of RP-6306 will proceed to the next higher dose level following BOIN criteria and dose escalation and de-escalation rules as follows:

- Dose escalation will progress with N≥2 patients with increases of up to 100% RP-6306 until a
 DLT is observed (Level R in Figure B and Table A below). Dose decisions will depend on 2 or
 more evaluable patients completing the first 2 14-day treatment cycles.

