RP-6306 will be supplied as immediate-release hard capsules for oral administration. RP-6306 will be orally self-administered with approximately 240 mL (~8 oz) of water after an overnight fast of at least 8 hours. Food and drink will be withheld for at least 1 hour after administration of RP-6306. Patients will be initially instructed to take their dose at approximately the same time in the morning. RP-6306 will be taken QD, on a continuous schedule in each 14-day cycle. If a BID dosing schedule is evaluated, the dose will be approximately an even split and should be taken 12 hours apart with food and drink withheld for at least 2 hours prior to and 1 hour post administration of the evening dose. If tolerability of RP-6306 is limited by continuous dosing, an intermittent dosing schedule of 3 consecutive days on / 4 consecutive days off may be explored as guided by the SRC and should follow the administration recommendations of the continuous schedule.

Irinotecan, leucovorin, and fluorouracil will be supplied as commercially available single-use vials. Initially, irinotecan will be administered IV at 180 mg/m² (100% of the approved dose level) given over 30 to 90 minutes on Day 1 of each 14-day cycle. Leucovorin will be administered concomitantly with irinotecan IV at 400 mg/m² (100% of approved leucovorin dose) given over 30 to 90 minutes on Day 1 of each 14-day cycle. Upon completion of the leucovorin infusion, a 400 mg/m² bolus of fluorouracil IV and then a 2400 mg/m² continuous infusion of fluorouracil (100% of approved fluorouracil dose) over 46 hours (Days 1 and 2 of each 14-day cycle) will be administered.

On Day 1 of each cycle, RP-6306 should be taken 15 minutes to 1 hour prior to the start of irinotecan and leucovorin.

During dose finding, intrapatient dose escalations are allowed at the discretion of the Investigator and with Sponsor approval. The dose of RP-6306 and/or irinotecan in the FOLFIRI regimen may be escalated to a higher dose level only after that dose level has been declared safe and tolerable by the SRC. Dose interruptions and dose reductions to manage toxicities will be allowed and carefully monitored by the Investigator, Sponsor, and SRC.

Duration of Treatment:

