3.2. Schedule of Assessments

The study will consist of a Screening Period (Day -28 to Day -1) to determine eligibility, Treatment Period (14-day cycles), End-of-Treatment (EOT) Period (occurring within 7 days after the last dose of study treatment), and a Safety Follow-up Period (occurring 30 days ±2 weeks after the last dose of study treatment for all patients not cleared at the EOT visit, including patients with ongoing Grade ≥2 drug-related toxicities at the EOT visit (Figure 2). The End of Study is defined as the date of the last visit (including all follow-up visits up to 12 months) of the last patient in the study. Patients will be followed for survival up to 12 months after EOT unless the patient withdraws consent to the study, the study is terminated, the patient dies or is lost to follow-up (LTFU).

Figure 2: Study Conduct

AE=adverse event; C1D1=Cycle1 Day 1; ctDNA=circulating tumor deoxyribonucleic acid; ECG=electrocardiogram; EOT=End-of-Treatment; FU=Follow-up; PD=progressive disease; PK=pharmacokinetic; RP2D=recommended Phase 2 dose.

The start of the study is defined as the date when the first patient in the whole study signs an informed consent form (ICF).

The end of the study is defined as the date of the last visit (including all follow-up visits) of the last patient in the whole study.

See protocol for full details on the schedule of assessments.

The key procedures required in this study include:

- Tumor assessments (based on CT, PET, and/or MRI scan) according to RECIST v1.1 or as clinically indicated (see Appendix 4 of the protocol)
- PK samples throughout the study
- Baseline, on-treatment, and EOT blood samples
- Reporting all AEs occurring from the administration of the first dose of RP-6306 and FOLFIRI
- Paired biopsies
- ECG

A cycle of treatment is 2 weeks (14 calendar days).

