- Dose escalation of RP-6306 will follow the BOIN criteria as guided by the SRC. RP 6306 can continue with increases of 20% to 50% (R+1).

Module 1b

[figure not shown]
If tolerability of continuous RP-6306 with FOLFIRI is limiting, Module 1b will be initiated if agreed upon by the SRC. In Module 1b, an intermittent dosing schedule of RP-6306 given 3 consecutive days on / 4 consecutive days off will be tested in combination with FOLFIRI. When Module 1b is initiated, the starting dose of RP-6306 and FOLFIRI will be the same as the highest total daily dose evaluated in Module 1a and will be given to a cohort of N≥2 patients. To allow better dose and schedule exploration early in the development, additional schedules may be evaluated that involve intermittent dosing (eg, 2 consecutive days on / 5 consecutive days off or 1 week on / 1 week off) depending on observed toxicities. The dose of RP-6306 or FOLFIRI will be increased or decreased per BOIN criteria independently of Module 1a until an MTD is established. Dose escalation decisions will be discussed with the SRC after at least 2 evaluable patients completing the first 2 14-day treatment cycles and based on the emerging safety and tolerability profile, and clinical PK/pharmacodynamic data across the entire patient population in Modules 1a and 1b.

In the event Modules 1a and 1b are explored concurrently, the Medical Monitor and SRC will prioritize slot allocation for each module. The highest dose level of RP-6306 in this study will not exceed the MTD

of RP-6306 monotherapy identified in the MYTHIC study for a given schedule. The totality of safety, PK, pharmacodynamic, and preliminary efficacy data will be used to select a preferred RP2D and schedule for RP-6306 and FOLFIRI.

If anti-tumor activity is observed at a dose level that is lower than the current dose level being explored (after escalation has proceeded to a higher dose level), additional patients (N≤6), preferably with the same tumor/genomic alteration, may be enrolled at the lower dose level to further confirm safety and efficacy at that dose level. The relevant DLTs from the backfill cohorts will be included in the MTD and RP2D determination by the SRC. Additionally, intrapatient dose escalations for patients at a lower dose level will be allowed at the discretion of the Investigator, and with Sponsor approval and guidance by the SRC, if the higher dose level was deemed safe by the SRC.

Figure 3: Module 1a and 1b Escalation Schema

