5. DATA AND ANALYSIS CONSIDERATIONS

5.1. General Principles

All demography and safety data will be presented by the safety population, except for the DLT reporting which will be based on the DLT evaluable population. Assessment of anti-tumor activity will be based on the Efficacy Population and PK data will be presented by the PK Population.

Most of the analyses will be descriptive in nature. Unless stated otherwise, continuous variables will be summarized using descriptive statistics (number of patients, mean, standard deviation, median, lower and upper quartile, minimum and maximum values) and the number and percentage of patients will be used for categorical variables. In general, missing data will be considered as missing and will not be imputed. Unless stated otherwise, percentages will be calculated out of the number of patients in the relevant analysis population.

Baseline will be the last assessment of the variable under consideration prior to first dose of RP-6306.

Unless stated otherwise, safety and efficacy data will be presented by assigned dose/schedule.

After determination of RP2D dose(s), safety and efficacy data may also be summarized by grouping dose levels based on RP2D and clinical relevance.

All DLT rates will be summarized by the assigned initial dose levels.

Summary statistics will be presented to the following degree of precision unless otherwise specified:

	Degree of Precision
Mean, Geometric mean, Median, Quartiles, Confidence limit boundaries	One more decimal digit than the raw data.
Standard deviation, Standard error	Up to 2 more than the raw data
Minimum, Maximum	The same decimal digit as the raw data.
Percentage	One decimal place. A percentage of 100% will be reported as 100%. Percentages of zero will be reported as 0.

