9. PHARMACOKINETIC (PK) PARAMETERS DATA

All PK data will be presented based on the Pharmacokinetic Population and presented by module 1a or 1b and dose/schedule.

PK parameters for RP-6306, irinotecan and SN-38 will be calculated using noncompartmental analysis (NCA) or population PK modeling. In summaries of raw concentration data, plasma concentration that falls below the lower limit of quantitation (BLQ) will be treated as zero in data tabulation. In individual PK parameter estimation, BLQ plasma concentrations will be treated as zero if the value preceded T_{max}. BLQ plasma concentrations will be treated as missing if the value occurs after T_{max}. All BLQ concentration values will be listed as reported.

PK concentrations and parameters will be listed for all patients in the PK population.

Individual patient and mean plasma concentration-time profiles will be plotted on linear and semi-logarithmic scales for each cohort and dose/schedule.

The following summary statistics will be presented for $AUC_{0\text{-last}}$, C_{max} , T_{max} , terminal elimination rate constant (Kel), and terminal elimination half-life (t½) for RP-6306, irinotecan and SN-38. $AUC_{0\text{-}8h}$, $AUC_{0\text{-}24h}$ (for QD dosing), $AUC_{0\text{--}12h}$ (for BID dosing) will be calculated for RP-6306 only. Other parameters maybe calculated to support the development of RP-6306. The PK parameters will be calculated using Phoenix WinNonlin version 8.3 or higher (Certara USA, Inc., Princeton, NJ) or other

appropriate software as appropriate. Default reporting in text and tables is 3 significant figures except for time related parameters ($t_{1/2}$, and T_{max}). Time related parameters will be reported to two decimal places.

PK parameters for RP-6306, irinotecan and SN-38 will be derived using non-compartmental methods from the concentration--time profiles as follows:

 Table 6:
 Derivation of Pharmacokinetic Parameters Prior to Analysis

Parameter	Definition	Method of Determination	
C _{max}	Maximum observed concentration within the dosing interval	Observed directly from data	
t_{max}	Time to C _{max}	Observed directly from data as time of first occurrence	
AUC _{0-last}	Area under the plasma concentration-time curve from time 0 to t ("t" being the longest time interval evaluable in all periods)	Linear up/Log down method	
AUC _{0-8h}	Area under the plasma concentration-time curve from time 0 to 8 hours post dose	Linear up/Log down trapezoidal method	

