AUC _{0-12h}	Area under the plasma concentration-time curve from time 0 to 12 hours post dose	Linear up/Log down trapezoidal method	
AUC _{0-24h}	Area under the plasma concentration-time curve from time 0 to 24 hours post dose	Linear up/Log down trapezoidal method	
t _{1/2}	Elimination half-life	Ln (2)/k _{el} , where k _{el} is the terminal phase rate constant calculated by a linear regression of the log-linear concentration-time curve	

PK parameters will not be calculated for profiles with less than three quantifiable concentrations. Actual PK sampling times will be used in the derivation of PK parameters.

For PK parameters on the respective cycles and days appropriate to a given dose and schedule, the following will be calculated:

- The geometric mean (gmean, calculated as exp $[\mu]$, where μ is the mean of the data on a logarithmic scale).
- Coefficient of variation (CV, calculated as CV =100*SD/mean], where SD is the standard deviation of the untransformed data).]).
- Geometric Coefficient of Variation calculated using log transformed data (Geom CV)
- Arithmetic mean calculated using untransformed data.
- Standard Deviation (SD) calculated using untransformed data.
- Minimum.
- Median.
- Maximum.
- Number of observations (n).

 T_{max} will be summarized as median, minimum, maximum and number of observations (n). -For summary statistics and summary plots by sampling time, the nominal PK sampling time will be used, for individual patient plots by time, the actual PK sampling time will be used.

Given that no formal hypothesis testing is being undertaken for this module, no statistical inference will be made.

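### SAP 4.4 labels PK patients by initial dose and Section 9 does not say otherwise, so read literally, profiles taken after a dose change are summarised under a dose no longer being taken

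*SAP*

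**What the plan says.** Three places in the SAP bear on which dose labels a PK result.

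- Section 4.4 (Pharmacokinetic Population) closes with "For all analysis populations, patients will be presented by the initial dose received". PK is not exempted, although the sentence stands in the PK section.
- Section 5.1 (General Principles) gives a labelling rule for other data: "Unless stated otherwise, safety and efficacy data will be presented by assigned dose/schedule". PK is not named there.
- Section 9 says "All PK data will be presented based on the Pharmacokinetic Population and presented by module 1a or 1b and dose/schedule" and later "For PK parameters on the respective cycles and days appropriate to a given dose and schedule, the following will be calculated". Neither sentence says whether the dose is the one first received or the one being taken at sampling. Section 9 has no rule to exclude, flag or dose-normalise a profile taken after a change.

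The documents foresee dose changes within a patient. SAP 3.2.1 states that "intrapatient dose escalations for patients at a lower dose level will be allowed at the discretion of the Investigator", subject to Sponsor approval and SRC guidance. The protocol synopsis names one such move: "patients treated at Dose Level 1 will be eligible to receive RP-6306 at 120 mg QD", from a start of 40 mg, once Dose Level 2 has completed its DLT period and the SRC agrees. Under Investigational Product, the synopsis also lets the irinotecan dose be escalated within a patient, and adds: "Dose interruptions and dose reductions to manage toxicities will be allowed and carefully monitored".

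On timing, SAP 3.2 lists "PK samples throughout the study" among the key procedures. The visit-level PK schedule is not in the available text.

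**The concern.** Keeping a patient under the starting dose is a reasonable convention for adverse events, and SAP 7.1 adopts it openly. A plasma concentration is different, because it reflects the dose taken before that sample. If the 4.4 rule is applied to PK, a profile measured on one dose appears in the row for another.

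PK parameters are a secondary endpoint, and PK is one of the named inputs to the RP2D and schedule. Dose groups are small (Dose Level 1 opens with up to 2 patients), so a single mislabelled profile can move a group summary noticeably. An escalation pushes the row up and a reduction pulls it down. Either way the planned SD, CV and geometric CV would count a dose difference as between-patient variability.

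**Working it through.** **Step 1: which sentence sets the dose label for PK?** No published figure is at issue, so this is a comparison of text.

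| Place | Data covered | Label stated |
|---|---|---|
| SAP 4.4 | all populations, PK included | initial dose received |
| SAP 5.1 | safety and efficacy | assigned dose/schedule |
| SAP 7.1 | adverse events after a dose modification | initial dose group |
| SAP 9 | PK | module and dose/schedule; initial or actual not stated |

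Section 4.4 is the only place that attaches a defined dose to a PK patient. Section 9 neither repeats nor overrides it.

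**Step 2: when could the named escalation happen?** Dose Level 2 opens after 2 or more evaluable Dose Level 1 patients complete 28 days, and it then needs its own 28 days. For those first patients the earliest day at 120 mg is 28 + 28 + 1 = Day 57. With 14-day cycles, four cycles end on Day 56, so this is Cycle 5 Day 1. Only profiles from Cycle 5 onward could be affected by this move. Dose reductions have no such lower limit in time.

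**Step 3: size, as an illustration.** Assume that exposure is proportional to dose, that patients are otherwise alike, and that k of the n profiles in one visit's summary row were taken at r times the labelled dose. Then:

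- geometric mean multiplier = r^(k/n)
- arithmetic mean multiplier = 1 + (r − 1)k/n

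| Change | r | k of n | Geometric | Arithmetic |
|---|---|---|---|---|
| 40 to 120 mg | 3 | 1 of 6 | 3^(1/6) = 1.20 | 1 + 2/6 = 1.33 |
| 40 to 120 mg | 3 | 1 of 2 | 3^(1/2) = 1.73 | 1 + 2/2 = 2.00 |
| 40 to 120 mg | 3 | 2 of 2 | 3.00 | 3.00 |
| increase of 50% | 1.5 | 1 of 2 | 1.5^(1/2) = 1.22 | 1 + 0.5/2 = 1.25 |
| reduction of 25% | 0.75 | 1 of 2 | 0.75^(1/2) = 0.87 | 1 − 0.25/2 = 0.88 |
| no post-change profile | any | 0 of n | 1.00 | 1.00 |

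The ratio of 3 is the documents' own 120/40. The 50% and 25% changes are examples, and the values of k and n are assumptions throughout.

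**Step 4: what is untouched.** DLT decisions rest on the first 28 days and on counts of patients with DLTs, not on PK tables. The PK criteria named for considering BID dosing are a half-life below 12 hours and a Cmax:Cmin ratio above 10. Under linear kinetics, multiplying a whole profile by r leaves both unchanged.

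**The case against.** The best defence is that Section 9 is the specific text and 4.4 the general one. Summarising parameters on the cycles and days that suit a given dose and schedule can naturally be read as requiring each profile to belong to the dose it is shown under. No precedence rule makes 4.4 prevail. This reading is available and stands as a possibility. It is not stated, however, and 4.4 says something different without exempting PK, so two programmers could build different tables from the same plan.

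Other parts of the defence also stand:

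- Whether serial samples exist after a dose change cannot be seen. A single list entry about sampling throughout the study does not establish it, and a profile needs at least three quantifiable concentrations to yield parameters.
- Because summaries are by cycle and day, a late profile at 120 mg would not be mixed with Cycle 1 or 2 profiles at 40 mg. Any mixing is confined to patients sampled at the same visit.
- The PK analysis is descriptive. Individual concentrations and parameters are listed and individual profiles are plotted, so an outlying profile could be noticed. Population PK and exposure-response work lies outside the SAP.

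These points limit the frequency and the consequences. They do not remove the need to say which dose labels the row.

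A reader might go further and infer that the BID decision would be biased. The documents do not support this, for the reason in Step 4. The protocol also ties that decision to PK at the initial dose levels and to emerging monotherapy data.

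**Conclusion.** The plan states one labelling rule for PK, and taken at its word it gives the wrong dose for any profile drawn after a permitted escalation or reduction. Section 9 leaves room for the right reading without adopting it. The affected outputs are the descriptive Cmax, AUC and variability summaries by dose for RP-6306, irinotecan and SN-38, and through them one of several inputs to the RP2D.

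The size is unknown because the number of post-change profiles is unknown. The range runs from no effect, if none are collected, to a geometric mean multiplied by 1.20 (1 of 6) or 1.73 (1 of 2) for a change from 40 to 120 mg. Those factors assume dose proportionality and are illustrations, not predictions.

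A reader might infer that the SAP certainly averages 120 mg data into the 40 mg row, or that dose selection as a whole is compromised. Neither follows: the first depends on an unseen sampling schedule and on 4.4 being applied over Section 9, and the second ignores that the DLT and MTD rules do not use these tables.

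**What to change.** Two edits to the SAP:

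1. In 4.4, exempt PK concentrations and parameters from the closing sentence.
2. In Section 9, state that PK concentrations and parameters are grouped by the RP-6306 dose and schedule in effect at the sampled dose and, for irinotecan and SN-38, by the irinotecan dose in effect at that point. Flag post-change profiles in the listings.

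With that grouping, the multiplier in Step 3 is 1.00 by construction. No sample size, dose rule or safety table changes.

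The cost is a little more programming and some smaller groups, since post-change profiles form their own rows. The actual RP-6306 dose levels are already used in the exposure derivation in 7.2. For irinotecan, 7.2 presents only duration and number of infusions, so the team should confirm that the dose given at each infusion is available to the PK dataset.
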